03 AUG 2018

Sponsor's Representative

Date

[name]
Director, Medical Science Department
Product Development Division
Taiwan Liposome Company, Ltd.

SYNOPSIS

Name of Sponsor/Company: Taiwan Liposome Company, Ltd. (TLC)	
Name of Finished Product: TLC599	
Name of Active Ingredient: Dexamethasone sodium phosphate (DSP)	
Title of Study:	A Phase IIa, Randomized, Double-blinded, Placebo-controlled, Dose-finding Study for Single-dose Administration of TLC599 in Patients with Osteoarthritis (OA) of Knee
Protocol No:	TLC599A2003
Study Sites:	Global study, around 8 to 13 sites
Study duration: The study will be conducted for approximately 27 weeks including a 21-day screening period and a 24-week follow-up period.	Phase: IIa

Objectives:
 
Primary: The primary objective is to evaluate the treatment efficacy of different test doses of TLC599 in patients with OA pain of knee.
 
Secondary: The secondary objective is to evaluate the safety of different test doses of TLC599 in patients with OA of knee.
 
Pharmacokinetics: The concentrations of dexamethasone and dexamethasone 21-phosphate in the synovial fluid at the end of study (EOS) or early termination (ET).
	
Methodology: This is a Phase IIa, multi-center, double-blind, prospective, randomized, placebo (normal saline)-controlled study, intending to explore the treatment efficacy of 2 different dose levels of TLC599 compared to the placebo in patients with OA of the knee.	
Planned number of patients:	Approximately 24 patients in each of 3 different study groups (a total of approximately 72 patients) will participate in the study.
Diagnosis and main criteria for inclusion:	
Main Criteria for inclusion
 
Before the start of any screening procedure, all patients must have signed an informed consent form and be willing to follow the procedures as described in the protocol.
 
 (1) Male or female patients, at least 50 years of age. (2) Has any symptoms associated with OA of the knee for at least 6 months prior to the screening visit and confirmation of OA based on the clinical and radiological criteria of American College of Rheumatology Criteria for Classification of Idiopathic OA of the knee (standing fixed-flexion posteroanterior X-ray of the knee of approximately 20 degrees) within 6 months prior to the screening visit or during the screening period. (3) The study knee has OA with Grade 2 to 3 severity based on the Kellgren-Lawrence grades according to confirmatory X-ray result in inclusion criterion 2. (4) Patients with patient related visual analogue scale (VAS) score of 5.0 to 9.0 of study knee prior to the study drug administration at

	
baseline. The VAS score of study knee should be equal or higher than non-study knee.
 
Note: If the patient has been confirmed to have OA for one knee but the VAS score of this knee is lower than the other knee which was not diagnosed with OA, the patient should be excluded and screened failure.
 
(5) Willing and able to comply with study procedures and provide written informed consent.
 
Main Criteria for exclusion
 
(1) Patients who received systemic corticosteroids within the last 30 days prior to study drug administration.
 
(2) Patients who start new rehabilitation or exercise program during screening period.
 
(3) Patients using glucosamine or chondroitin or dietary supplement with unstable dose or frequency within 4 weeks before screening visit.
 
(4) Patients who use prohibited medications within 7 days prior to study drug administration or any pain control medication including acetaminophen within 48 hours prior to study drug administration.
 
(5) Patients who use prohibited medications other than acetaminophen and oral NSAIDs from screening visit to 7 days prior to study drug administration.
 
(6) Documented history and confirmed autoimmune disease including but not limited to secondary OA, Reiter's syndrome, systemic lupus erythematosus, Sjögren's syndrome, systemic sclerosis, inflammatory myositis, mixed connective tissue disease, palindromic rheumatism, reactive arthritis, rheumatoid arthritis, psoriatic arthritis, ankylosing spondylitis, Bechet's disease, arthritis associated with inflammatory bowel disease, sarcoidosis, vasculitis, cryoglobulinemia, or amyloidosis.
 
(7) Evidence of intra-articular bleeding of the study knee at baseline prior to study drug administration.
 
(8) History of infective arthritis in the study knee, or suspected / concurrent infection in the study knee at baseline prior to study drug administration.
 
(9) Documented gout attack in study knee within 6 months, evidence of tophi formation, or active gouty arthritis attack prior to the baseline.
 
(10) Patient with any amputation in any lower limb.
 
(11) Any condition that could possibly confound the patient's assessment of study knee pain in judgement of the investigator (i.e., ipsilateral hip OA, radicular low back pain, and hip pain refer to the study knee).

--	--

	
(12) Unstable study knee joint as determined by the investigator based on physical examination (with or without buckling or giving way) due to an acute injury (defined as injury within 6 months, eg. anterior cruciate ligament injury or tear); OR any surgery or arthroscopy in the study knee within the 12 months prior to the screening visit.(13) Clinical symptoms and signs of acute infection or infection-related inflammation in the other knee before study drug administration.(14) Use of IA corticosteroid, hyaluronic acid, or other IA injection in the study knee within 3 months prior to the screening visit.(15) Any skin lesion / breakdown at the anticipated injection site or any condition that impairs penetration of the study knee joint space.(16) Patient with body mass index > 40 kg/m² at the screening visit.(17) Platelet count < 80,000/μL, or blood coagulation disorders, including patients with hemophilia, decompensated liver cirrhosis or uremia at the screening visit.(18) History of acquired or congenital immunodeficiency diseases.(19) Concurrent systemic active or uncontrolled infectious disease.(20) A history of treated malignancy which is disease free for \leq 5 years prior to the screening visit, except basal-cell carcinoma of skin or carcinoma-in-situ of the uterine cervix.(21) Stroke or myocardial infarction within 3 months prior to the screening visit.(22) Uncontrolled and unstable concurrent medical or psychiatric illness, including but not limited to, poorly controlled diabetes (defined as HbA1c > 9.0%), poorly controlled hypertension (mean arterial pressure [2/3 diastolic blood pressure + 1/3 systolic blood pressure] > 110mmHg), severe dementia, schizophrenia, or bipolar disorder, that will jeopardize the safety of the patient, interfere with the objectives of the protocol, or affect the patient compliance with study requirements, as determined by the investigator.(23) Patients with a condition or in a situation which, in the assessment of the investigators, will interfere with the patient's ability to comply or cooperate with the dosing and visit schedules and the protocol evaluations or may not be suitable for this study (e.g. illiterate).(24) Use of any chemotherapeutic or systemic immunosuppressant agents for inflammatory diseases within 6 months prior to the screening visit.(25) Current use of anticoagulants, including warfarin, heparin, low-molecular weight heparin, or dabigatran.(26) Use of any investigational agent within 4 weeks prior to study drug administration or within 5 half-lives of the product, whichever is
--	---

	
longer.
 
(27) Known allergy or hypersensitivity to the study drug or its components.
 
(28) Female patients who are pregnant, nursing, planning to become pregnant, or who are of childbearing potential (defined as all the female patients after puberty, unless they have been post-menopausal for at least 2 years, are sterile based on a documented ovarian failure, or are surgically sterile, such as after hysterectomy, bilateral oophorectomy, or bilateral tubal ligation) and not using reliable means of contraception (e.g. established use of oral, transdermal, injected or implanted hormonal methods of contraception, placement of an intrauterine device or intrauterine system, barrier methods of contraception, male sterilization, total abstinence, etc.).
 
(29) Abnormalities of laboratory parameters as described below will qualify for exclusion at the screening visit:
 
 • hemoglobin < 8 g/dL; • total white blood cell count < 4000/ μL; • serum bilirubin/ alanine aminotransferase/ aspartate aminotransferase > 2 times upper limit of normal (ULN) for the laboratory reference ranges; • eGFR <30 ml/min; • prothrombin time / International Normalized Ratio > ULN for the laboratory reference range. 
(30) Contraindication to undergoing magnetic resonance imaging (MRI) for both knees including but not limited to pacemaker, metal sutures, presence of shrapnel or iron filings.

Test product, dose and mode of administration:
	
Test product: TLC599
 
(1) low-dose group: 12 mg DSP with 100 μmol PL (1.0 mL) via intra-articular injection;
 
(2) high-dose group: 18 mg DSP with 150 μmol PL (1.5 mL) via intra-articular injection.

Reference therapy, dose, and mode of administration:
	
Placebo group: Normal saline 1.5 mL via intra-articular injection

Criteria for evaluation:

Primary Endpoint:

The primary endpoint is to evaluate the change from baseline by Western Ontario and McMaster Universities Osteoarthritis Index (WOMAC) pain subscale through Week 12.

Secondary Endpoints:

- (1) Change from baseline to Weeks 1, 4, 8, 12, 16, 20, and 24 in the patient rated visual analogue scale (VAS), and pain / function subscales of WOMAC.
- (2) Change from baseline through Weeks 12, 16, 20 and 24 in VAS, and pain / function subscales of WOMAC
- (3) Area under the effect curve (AUEC) of the VAS from baseline to Week 12, 16, 20 and 24.
- (4) Area under the effect curve of the WOMAC pain subscale from baseline to Week 12, 16, 20 and 24.
- (5) Proportion of responders by a decrease of > 30% or > 50% in patient-rated VAS from baseline to Weeks 1, 4, 8, 12, 16, 20, and 24.
- (6) Proportion of responders by a decrease of > 30% or > 50% in WOMAC pain subscale from baseline to Weeks 1, 4, 8, 12, 16, 20, and 24.
- (7) Proportions of durable responders with persistent response since Week 1 till Weeks 12, 16, 20, and 24, respectively, by pain relief > 30% in VAS.
- (8) Proportions of durable responders with persistent response since Week 1 till Weeks 12, 16, 20, and 24, respectively, by pain relief > 30% in WOMAC pain subscales.
- (9) Proportions of durable responders with persistent response since Week 1 till Weeks 12, 16, 20, and 24, respectively, by outcome measured in rheumatology- Osteoarthritis Research Society International set of responder criteria.
- (10) Change from baseline to Weeks 1, 4, 8, 12, 16, 20, and 24 in EuroQol-5 Dimension questionnaire.
- (11) Total consumption of acetaminophen at Weeks 1, 4, 8, 12, 16, 20, and 24.
- (12) Safety and tolerability.

Pharmacokinetic Endpoints:

The concentrations of dexamethasone and dexamethasone 21-phosphate in synovial fluid of the study knee joint at end of study or early termination.

Statistical methods:

Sample size calculation:

This is an exploratory study and there is no formal sample size evaluation. It is expected to have approximately 20 patients in each study groups completing 24-week follow-up period after study drug administration. Given a drop-out rate of 15%, approximately 24 patients in each study group will be enrolled and a total of approximately 72 patients will be randomly assigned.

General statistical considerations:

All efficacy and safety variables will be summarized using descriptive statistics. Continuous variables will be presented as number of observations, mean, standard deviation, median and range; while categorical variables will be presented as number of observations, count, and percentage in frequency table.

In this study, safety population is used for any safety analysis. The intent-to-treat (ITT), modified Intent-to-treat (mITT) and per-protocol (PP) populations will be used in analysis of efficacy variables, but the major efficacy conclusion will be based on the results obtained from mITT population. The analysis of

dexamethasone and dexamethasone 21-phosphate concentrations in the synovial fluid will be conducted based on the pharmacokinetic (PK) population.

Unless otherwise specified, all statistical assessments will be 1-sided and evaluated at the 5% level of significance.

All analyses, summaries, and listings will be performed using statistical analysis software (Version 9.2 or higher).

Further details regarding the definition of analysis variables and analysis methodology will be specified in a statistical analysis plan (SAP) to address all study objectives. The SAP will be developed and approved before database lock.

Analysis population:

The populations for analysis applied into this study are defined as follows:

- (1) Intent-to-treat population: all enrolled and randomized patients.
- (2) Safety population: All patients who receive any dose of study drug administration will be included in the safety population.
- (3) Modified Intent-to-treat population: The mITT population indicates all enrolled patients who receive one complete dose of study drug administration and have at least one complete efficacy evaluation after study drug dosing.
- (4) Per-protocol population: The PP population is a subset of mITT population fulfilling evaluable criteria without any major protocol deviation and has evaluation at baseline, Week 12 and at least 2 other evaluation within 12 weeks.
- (5) Pharmacokinetics population: All ITT patients who receive any dose of study drug, and those who consented for synovial fluid collection from the study knee at the end of study (EOS)/early termination (ET) visit.

Efficacy analysis:

All efficacy analyses will be conducted for the mITT and PP populations as well as ITT population.

For the primary efficacy analysis, the overall change from baseline in WOMAC pain subscale over 12 weeks will be analyzed using a mixed-effects model for repeated measures (MMRM) with restricted maximum likelihood estimation. The model will include factors of treatment, visit (as a categorical variable), baseline value of the WOMAC pain subscale score as fixed factors, site as random factor, and treatment-by-visit as interaction terms. This methodology will be used to compare treatment groups for change from baseline through Week 12. The model estimates by treatment group, contrast estimates for between-group (pairwise) comparisons, standard errors, 90% CIs, and p-values will be presented.

An MMRM model as described for primary efficacy analysis will be used to analyze the overall change from baseline in WOMAC pain / function subscale and VAS over 12, 16, 20 and 24 weeks as well as the change from baseline in WOMAC pain / function subscale and VAS at each scheduled visit.

Analysis of covariance (ANCOVA) is to be used for secondary efficacy endpoints measured in continuous scale, including treatment group, and the baseline value of that endpoint and the study sites as covariate if appropriate. Within each treatment group, the total consumption of acetaminophen, changes from baseline in patient-rated VAS, WOMAC pain subscale, WOMAC function subscale, and EQ-5D at scheduled time points, and AUEC of VAS/WOMAC pain subscale will be summarized using descriptive statistic and estimated using the least squares mean. The 2-sided 90% confidence interval for LSM will be reported for each treatment arm.

The frequency and percentage will be used to summarize patients achieving the response criteria at scheduled time points and patients achieving the durable response criteria and will be presented by treatment group. Treatment comparisons of each TLC599 dose treatment with placebo will be made using a logistic regression analysis with treatment group, study site, and the baseline value of that endpoint as covariate in the model.

Explorative univariate models will be used to identify the possible prognostic factors associated with

WOMAC pain subscale and VAS, e.g. age, gender, race, unilateral or bilateral knee pain, and baseline severity by VAS or pain score and Kellgren-Lawrence grades. The subgroup analysis will be performed according to the results of regression model.

Safety analysis:

The assessment of safety will be based mainly on the frequency of adverse events (AEs), which includes all serious AEs (SAEs) and AEs, clinical laboratory data, vital signs, physical examination, electrocardiogram (ECG) result, articular cartilage assessment by MRI, and other safety findings.

All safety variables will be summarized using descriptive statistic based on the safety population. No inferential statistics are planned.

Pharmacokinetics analysis:

The concentrations of dexamethasone and dexamethasone 21-phosphate in the synovial fluid of the study knee at EOS will be summarized by treatment group using descriptive statistics.

Schedule of Events

Visit	Screening	1(Baseline)	2	3	4	5	6	7	8	EOS/E T
Week/Day	Day -21 ~ -1	Day -1 ~ 0	Day 3	Week 1	Week 4	Week 8	Week 12	Week 16	Week 20	Week 24
Window (day)			± 1	± 3	± 3	± 3	± 3	± 3	± 3	± 3
Informed consent	X									
Inclusion/exclusion criteria	X	X								
Demographics and medical history	X									
Physical examination and vital signs ¹	X	X	X	X	X	X	X	X	X	X
X-ray examination ²	X									
Clinical chemistry and hematology ³	X	X	X	X	X	X	X	X	X	X
Urinalysis	X									X
12-lead ECG	X									X
HbA1c	X						X			X
Blood cortisol ⁴		X	X	X	X	X	X	X	X	X
Urine pregnancy test ⁵	X	X								X
VAS Score ⁶		X	X	X	X	X	X	X	X	X
WOMAC score ⁶		X	X	X	X	X	X	X	X	X
EQ-5D ⁶		X	X	X	X	X	X	X	X	X
Randomization ⁶		X								

Visit	Screening	1(Baseline)	2	3	4	5	6	7	8	EOS/ET
Week/Day	Day -21 ~ -1 1	Day -1 ~ 0	Day 3	Week 1	Week 4	Week 8	Week 12	Week 16	Week 20	Week 24
Window (day)			± 1	± 3	± 3	± 3	± 3	± 3	± 3	± 3
Excessive synovial fluid aspiration / analysis & Study drug administration ^{6,7,}		X								
MRI examination ⁸	X									X ⁹
Concomitant medication	←									
AE/SAE	←									
Diary card ¹⁰	←									
Pharmacokinetics samples collection (synovial fluid) (optional) ¹¹										X

- Height is measured only at screening. Weight is measured at screening, Visit 1, 4, 5, 6, 7, 8 and EOS/ET. Vital signs including BP, HR, RR, tympanic temperature will be assessed at each follow-up visit.
- The X-ray examination will include a chest PA view and examination for both knees, if it has not been performed during the 6 months prior to screening.
- view of X-ray examination will be performed for both knees, if it has not been performed during the 6 months prior to screening.
INR of PT and aPTT should be performed at the screening visit only. HbA1c should be performed at screening visit, Visit 6 and the EOS/ET visit. Other laboratory tests (clinical chemistry and hematology) at Visit 1 will be performed before study drug administration. Fasting glucose examination is not required for the screening visit, but will be required for all subsequent visits, from Visit 1 to EOS/ET visit.
- A blood sample to measure the plasma or serum cortisol level should be collected before 10:00 am or based on local lab requirement at the scheduled visits and before study drug administration at Visit 1.
- Urine pregnancy tests will be performed only for women with childbearing potential.
- At Visit 1, some local sites may have facility constraint for study drug preparation. Randomization, VAS, WOMAC, and EQ-5D questionnaires should be performed at the same day. Study drug administration is allowed to be performed at the same day as randomization or one day after randomization. The day of study drug administration is defined as Day 0.
- For patient with excessive synovial effusion, it is accepted to aspirate the excessive synovial fluid during study drug administration procedure. However, the characteristic and amount of the aspirated fluid should be recorded. The aspirated fluid can be sent for laboratory examination if there is any concern of infection, intra-articular bleeding or the OA diagnosis is questionable.
- For the articular cartilage evaluation of the knees, all subjects should have MRI examination conducted for MOAKS grading during the screening period or prior to randomization, and at the end of study/early termination. MRI images will be performed for both knees.
- MRI examination can be performed within 21 days prior to EOS/ET visit.

10. Use of acetaminophen will be recorded on diary card.
 11. Synovial fluid from the study knee will be collected after completion of efficacy evaluation (VAS, WOMAC and EQ-5D) at EOS or within 3 days after ET visit, only if the subject has provided written informed consent for this procedure. In addition, it will only be aspired if appropriate synovial fluid volume in the study knee is ensured by local ultrasound examination and/or at the investigator's discretion prior to the aspiration.
- Abbreviations: AE=adverse event; BP=blood pressure; ECG=electrocardiogram; EOS=end of study; EQ-5D=EuroQol-5 Dimension; ET=early termination; HbA1c=glycosylated hemoglobin; HR=heart rate; INR= international normalized ratio; MOAKS=MRI Osteoarthritis Knee Score; MRI=magnetic resonance imaging; PA=posterior-anterior; PT=prothrombin time; aPTT=partial thromboplastin time; RR=respiratory rate; SAE=serious adverse event; VAS=visual analogue score; WOMAC=Western Ontario McMaster Universities.

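### Does it matter that the plan does not say whether Day 3 counts in the primary 12-week WOMAC pain contrast?

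*Combined protocol and SAP*

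**What the plan says.** The primary endpoint in the synopsis has a time horizon but no visit list: "The primary endpoint is to evaluate the change from baseline by Western Ontario and McMaster Universities Osteoarthritis Index (WOMAC) pain subscale through Week 12". The Efficacy analysis section repeats the horizon ("the overall change from baseline in WOMAC pain subscale over 12 weeks will be analyzed using a mixed-effects model for repeated measures (MMRM") and puts in the model treatment, "visit (as a categorical variable), baseline value of the WOMAC pain subscale score as fixed factors", site as a random factor, and the treatment-by-visit interaction. It gives no contrast coefficients.

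Other parts of the document bear on Day 3:

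- The Schedule of Events marks WOMAC at baseline and at every later visit, including Day 3.
- Secondary endpoint (1) names its time points and begins at Week 1: "Change from baseline to Weeks 1, 4, 8, 12, 16, 20, and 24 in the patient rated visual analogue scale (VAS" and the WOMAC pain and function subscales. The responder, EQ-5D and acetaminophen endpoints use the same weeks, and durable response is counted from Week 1.
- The paragraph on the secondary MMRM analyses covers the 12-, 16-, 20- and 24-week overall changes "as well as the change from baseline in WOMAC pain / function subscale and VAS at each scheduled visit".
- Secondary endpoint (4) is a separate time-weighted summary: "Area under the effect curve of the WOMAC pain subscale from baseline to Week 12, 16, 20 and 24".
- General statistical considerations states: "Further details regarding the definition of analysis variables and analysis methodology will be specified in a statistical analysis plan (SAP", to be approved before database lock.

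**The concern.** With a treatment-by-visit interaction there is no single treatment effect. An overall effect is defined only once its visits and weights are fixed, and the synopsis fixes neither. Read literally, the phrase about scheduled visits brings Day 3 in; the endpoint lists leave it out. Two statisticians could both follow the text and report different primary estimates.

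If Day 3 came in with the equal weights that a default least-squares mean would give, a visit three days after injection would count as much as Week 12. Day 3 and Week 1 together would make up 40% of a figure described as covering 12 weeks. An early effect that fades would then look larger, and a delayed one smaller, than the average over the period.

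**Working it through.** **Inputs.** Post-baseline WOMAC visits to Week 12 (Schedule of Events): Day 3 and Weeks 1, 4, 8 and 12, that is days 3, 7, 28, 56 and 84. Planned enrolment is 24 per arm (20/0.85 = 23.5, rounded up, which reproduces the plan's figure). The plan states no visit weight, so there is no figure of its own to reproduce on this point. Equal weights, a time-weighted yardstick and the effect profiles below are all assumptions.

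**Step 1: weights.** Equal weights are 1/5 = 20% each with Day 3, and 1/4 = 25% each without. Trapezoid weights on days 0, 3, 7, 28, 56 and 84, with zero change at day 0, are 3.5, 12.5, 24.5, 28 and 14 days, which sum to 82.5:

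| | Day 3 | Wk 1 | Wk 4 | Wk 8 | Wk 12 |
|---|---|---|---|---|---|
| Time share | 4.2% | 15.2% | 29.7% | 33.9% | 17.0% |
| Equal, with Day 3 | 20% | 20% | 20% | 20% | 20% |
| Equal, without | 0 | 25% | 25% | 25% | 25% |

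By elapsed days alone, Day 3 is 3/84 = 3.6%. In the 16-, 20- and 24-week contrasts its equal-weight share falls to 1/6, 1/7 and 1/8 (16.7%, 14.3%, 12.5%).

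Leaving Day 3 out does not make equal weights match time shares either: Weeks 1 and 12 become too heavy and Weeks 4 and 8 too light.

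**Step 2: what Day 3 does to the estimate.** Let d be the Day 3 effect and m the mean effect at Weeks 1, 4, 8 and 12. The five-visit mean minus the four-visit mean is (d + 4m)/5 - m = (d - m)/5. It is zero if the effect is constant. For assumed effects at Day 3 and Weeks 1, 4, 8 and 12:

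| Profile | With Day 3 | Without | Shift | Time-weighted |
|---|---|---|---|---|
| 0.5, 0.5, 0.4, 0.35, 0.3 | 0.410 | 0.3875 | +6% | 0.3855 |
| 0.4, 0.45, 0.4, 0.35, 0.3 | 0.380 | 0.375 | +1% | 0.3736 |
| 0.3, 0.5, 0.4, 0.3, 0.2 | 0.340 | 0.350 | -3% | 0.3430 |
| 0.6, 0.6, 0.4, 0.2, 0.1 | 0.380 | 0.325 | +17% | 0.320 |
| 0.1, 0.3, 0.5, 0.5, 0.5 | 0.380 | 0.450 | -16% | 0.4527 |

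The four-visit mean is closer to the time-weighted value in four of the five profiles, and the five-visit mean in the third.

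**Step 3: worst case.** For effects that only fall or only rise, the largest departure from the time-weighted mean comes from a step. A full effect at Day 3 and Week 1 and none from Week 4 gives 0.40 - (0.042 + 0.152) = 0.206 of the peak effect with Day 3 in. Without Day 3 the largest departure is 0.080: an effect that vanishes only at Week 12 gives 0.75 against 0.830. These are bounds for all-or-nothing steps, not expected values.

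**Step 4: size against noise.** Take the profiles as standard deviation units and assume compound symmetry, correlation 0.5 and complete data with 24 per arm. The standard error of the four-visit contrast is sqrt[(2/24) x (1 + 3 x 0.5)/4] = 0.228. The largest shift, 0.07, is 0.07/0.228 = 0.3 standard errors. The three milder shifts (0.0225, 0.005 and 0.010) are at most 0.1. The choice barely affects precision: the ratio of standard errors without to with Day 3 is sqrt{[(1 + 3r)/4] / [(1 + 4r)/5]}, which is 1.028 at r = 0.4 and 1.010 at r = 0.7.

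**The case for a change.** The best case for a change is that this is the primary estimate, that p-values and 90% intervals will be attached to it, and that one sentence would settle it. The text points both ways. The Day 3 window (±1 day) and the Week 1 window (±3 days) meet at day 4, so two of five equally weighted visits could be almost the same time point.

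The ambiguity stands: visits and weights should be on paper before the data are unblinded. But three parts of the argument weaken on inspection.

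- The text does not favour including Day 3. The phrase about scheduled visits sits in a sentence on secondary endpoints, and read with endpoint (1) it means the listed weeks. A categorical visit term does not say which levels enter. The Schedule of Events footnote that places synovial sampling "after completion of efficacy evaluation (VAS, WOMAC and EQ-5D) at EOS" concerns the final visit. On Day 3 the text is neutral.
- The comparison of 20% with 4% presumes that the MMRM summary ought to be time-weighted. The plan has a separate endpoint for that, and it does not list the time points of that curve either.
- A proposal to use Weeks 1, 4, 8 and 12 would itself accept Day 3 if its weight were stated. It therefore asks for a choice to be recorded and does not correct a wrong one.

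**Conclusion.** No change to the plan is needed. The synopsis is silent on which visits and weights form the overall contrast, but it contains no rule that gives a wrong result, and a mean over four visits or over five is a defensible estimand. Contrast coefficients are the kind of detail that the synopsis assigns to a SAP due before database lock. That detail is not in the text available here, so nothing shows that it was left open, and a statistician writing it would have to name the visits in order to program the contrast.

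The consequence is zero for a constant effect, a few percent for mild profiles, and 16-17% for the two steep ones. In the assumed standard deviation units that is at most about 0.3 of a standard error. These sizes rest on equal weights, the assumed profiles and, for the standard error, compound symmetry with complete data. The trial is exploratory with no formal sample size calculation, and the planned by-visit and area-under-the-curve results will show any early or late pattern that the single figure blurs.

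### The MMRM has no baseline-by-visit term, so late-visit contrasts can lose some precision if the baseline slope changes over follow-up; the primary 12-week average is little affected (minor)

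*Combined protocol and SAP*

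**What the plan says.** The Synopsis (Statistical methods, Efficacy analysis) specifies the primary model term by term. Besides treatment and categorical visit, it has "baseline value of the WOMAC pain subscale score as fixed factors, site as random factor, and treatment-by-visit as interaction terms". Treatment may therefore act differently at each visit, but baseline may not. The primary contrast is the overall change in WOMAC pain over 12 weeks.

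The next paragraph carries the model over to the secondary endpoints: "An MMRM model as described for primary efficacy analysis will be used to analyze the overall change from baseline" in WOMAC pain, WOMAC function and VAS over 12, 16, 20 and 24 weeks, and also for "the change from baseline in WOMAC pain / function subscale and VAS at each scheduled visit".

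The paragraph after that names a second method: "Analysis of covariance (ANCOVA) is to be used for secondary efficacy endpoints measured in continuous scale, including treatment group, and the baseline value". It lists changes in VAS and WOMAC at scheduled time points among the quantities to be estimated by least squares means. No rule says which method governs those change scores.

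The Schedule of Events collects WOMAC and VAS at baseline, Day 3 and Weeks 1, 4, 8, 12, 16, 20 and 24. The by-visit secondary endpoints start at Week 1, and the model description does not say whether Day 3 is included. The Synopsis leaves further methodological detail to a SAP to be approved before database lock.

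**The concern.** The outcome is change from baseline. With equal SDs over time, the slope of change on baseline at a visit is the baseline-to-visit correlation minus 1. If that correlation fades between Day 3 and Week 24, the true slope moves with it. A single slope estimated by generalised least squares is then a compromise. Under the decay patterns tried below it sits nearer the early, closely spaced visits and fits worst at the late ones.

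Two things follow at a late visit. Baseline explains less variance than it could, so the reported intervals are wider than they need be. And an arm that happens to start with more pain appears to improve more than it should, because the adjustment is too weak. With about 24 patients per arm such imbalances are routine. The Week 16-24 contrasts are also the ones that speak to duration of effect after a single injection.

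**Working it through.** **The plan's own figures.** The sample size paragraph expects 20 completers per arm and 15% drop-out: 20/(1 - 0.15) = 23.5, rounded up to 24, and 3 x 24 = 72. Both are reproduced. With 24 per arm, the typical (1 SE) chance difference in mean baseline between two arms is sqrt(2/24) = 0.29 baseline SD.

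**Assumptions.** The documents give no SD, correlation or covariance structure. SDs are taken as equal over time, Day 3 is modelled, there is no site effect and the covariance is unstructured. Two patterns are assumed for the correlation between measurements *d* days apart:
- exponential: 0.85 x exp(-*d*/90)
- decay to a floor: 0.3 + 0.5 x exp(-*d*/40)

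**Formulas.** The true slope at visit *t* is b_t = r_t - 1, where r_t is its correlation with baseline. The common slope is b* = (1'S⁻¹b)/(1'S⁻¹1), where S is the residual covariance under the common slope, solved iteratively. The slope error is e_t = b* - b_t. Then

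SE ratio = sqrt(1 + e_t² / (1 - r_t²)), and imbalance left = e_t x 0.29 SD.

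**Worked case: exponential, 12-week model (5 visits), Week 12.** r = 0.85 x exp(-84/90) = 0.334, so b_t = -0.666. The common slope is -0.288, so e = 0.378. SE ratio = sqrt(1 + 0.378²/0.888) = 1.077. Imbalance left = 0.378 x 0.29 = 0.11 SD.

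| Contrast | Exponential: e, SE increase | Floor: e, SE increase |
|---|---|---|
| Week 12, 12-week model | 0.38, 7.7% | 0.27, 4.2% |
| Week 12, 24-week model | 0.30, 5.1% | 0.22, 2.8% |
| Week 24, 24-week model | 0.51, 12.3% | 0.28, 4.1% |
| Primary average to Week 12 | 0.11, 2.1% | 0.07, 0.9% |

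Imbalance left at Week 12 runs from 0.22 x 0.29 = 0.06 SD to 0.38 x 0.29 = 0.11 SD. For the primary average it is 0.02-0.03 SD. Under compound symmetry every entry is zero.

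**Simulation check.** With 3 x 24 patients and 15% drop-out, empirical SD ratios at Week 12 were 1.08 (exponential) and 1.03 (floor). At Week 24 they were 1.11 and 1.06. This agrees with the table to within about 2 percentage points.

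**Other correlation patterns.** A separate simulation used 20 completers per arm, 4,000 trials per setting, and two residual correlation structures. The baseline correlation was flat or fell linearly from Day 3 to Week 24:

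| Baseline correlation | SE ratio, Week 24 | SE ratio, primary average |
|---|---|---|
| flat at 0.5 | 0.995-0.999 | 1.00 |
| 0.6 to 0.4 | 1.01 | 1.00 |
| 0.7 to 0.3 | 1.06-1.07 | 1.01-1.02 |
| 0.8 to 0.2 | 1.20-1.24 | 1.02-1.12 |

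The flat row shows the price of an unneeded term: at most about 0.5% of SE at Week 24.

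**Day 3.** Leaving Day 3 out of the 12-week model lowers the Week 12 loss from 7.7% to 5.7% (exponential) and from 4.2% to 2.7% (floor).

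**Scale.** A 12% larger SE corresponds to 1/1.12² = 0.80 of the information, or about 4 of 20 completers per arm. A 4% larger SE corresponds to 1/1.04² = 0.92, or about 1.5 of 20.

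**The case against.** The strongest reply is that the harm is assumed. A model with treatment, visit, treatment-by-visit and one baseline slope is valid, and nothing in the documents shows that the slope changes. Slope also depends on the SD ratio, not on correlation alone. Entry requires a study-knee VAS of 5.0 to 9.0 at baseline. That truncates baseline VAS, probably narrows baseline WOMAC pain, and could lower the early correlations. With an assumed correlation of 0.35 + 0.15 x exp(-*d*/40), the loss is 0.2% at Weeks 12 and 24 and nil for the primary average. With the floor pattern and a follow-up SD rising from 1.05 to 1.4 times baseline, the late-visit loss falls from about 4% to about 2%. All of this stands, and it is why the point is conditional and minor.

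It is also fair to say that the trial is exploratory with no formal sample size, that the larger losses fall on secondary contrasts, and that the ANCOVA, if fitted visit by visit, already gives each visit its own slope. The last point helps only partly: the plan then holds two different baseline assumptions for the same change scores and does not rank them. Deferral to a SAP does not settle the matter either, because the Synopsis already lists the model terms and the list would naturally carry over.

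A reader might infer that the primary analysis is biased or its test invalid. It is not. The retained imbalance depends on the baselines observed and averages to zero over randomisations, and the misfit enters the residual variance and so the reported SE. A reader might also infer a loss of 20% or more. That needs a correlation falling from 0.8 to 0.2, for which the documents offer no support.

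**Conclusion.** The omission is real: as described, one baseline slope applies from the first modelled visit to Week 24. Whether it costs anything depends on correlations that the documents do not give. Under the assumed moderate to exponential decay, with equal SDs and Day 3 modelled, the loss is modest at Week 12 and larger at Week 24. It is negligible under mild decay and nil under a constant slope. The primary 12-week average is largely protected, because the common slope is too steep for some of the visits averaged and too shallow for others, and these errors partly cancel. This is a minor efficiency point about secondary late-visit contrasts. It is worth acting on because the payoff is one-sided: almost nothing is lost if the term is not needed, and several percent of SE is recovered at the late visits if it is.

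**What to change.** Before database lock:

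1. Add baseline-by-visit to the primary MMRM and to every secondary MMRM built on it (WOMAC pain, WOMAC function and VAS, through Weeks 12, 16, 20 and 24 and by visit). Keep treatment, visit, treatment-by-visit, baseline and random site as planned.
2. State which visits enter each model, in particular whether Day 3 does.
3. State whether the MMRM or the ANCOVA governs the by-visit change scores, and label the other as supportive or remove it.

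The cost is one parameter per post-baseline visit beyond the first: 4 in the 12-week model and 7 in the 24-week model if Day 3 is included, 3 and 6 if it is not. If the slope is in fact constant, the SE rises by less than about 1%. No new data, no further patients and no change to the quantity being estimated are needed.
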